A minimum of one cohort containing two treatment arms (20 patients; 10 patients per arm) will be investigated with a maximum of 3 cohorts (60 patients; 3 dosing regimens; 2 arms; 10 patients per arm) being tested as shown in Figure 1. The starting dosing regimen for the first *P. vivax* or *P. falciparum* cohorts will be three consecutive daily doses of the combination of SJ733 (600 mg) and cobicistat (150 mg). Based on the results from completed Phase 1a/1b studies, this dose is expected to be well-tolerated and show complete clearance of parasites on Day 7 as determined by microscopy (thick blood smear) and a $\leq 20\%$ recrudescence rate as assessed by microscopy on Day 14.

If the data from the first cohorts of *P. falciparum* (cohort 1A) and *P. vivax* (cohort 1B) respectively meet the success criteria, two other dosing regimens, expected to yield reduced total exposures of SJ733, may be investigated. Each is expected to be efficacious. If data from the first cohorts are inconclusive, an adaptation will be triggered to use the same dosing regimen for a larger number of patients in order to improve statistical power and more accurately classify a potential failure. An inconclusive result will be defined at Day 14 as: 1) the absence of any repeated drug-related SAE; and 2) crude ACPR between 60-80% (equivalent to 20-40% recurrence). If data from the first cohorts result in failure, the trial will be stopped. Failure is defined as: 1) the detection of

any 2 incidents of the same drug-related SAE; or 2) crude ACPR < 60% (equivalent to > 40% recurrence).

Cohort 2 will test whether pharmacoenhancement of SJ733 with cobicistat is required for clinical efficacy. If cohort 2 meets the success criteria, the trial will be complete. If data from cohort 2 are inconclusive, an adaptation will be triggered to use the same regimen for a larger number of patients in order to improve statistical power and more accurately classify a potential failure. If cohort 2 proves safe (no repeated drug-related SAE) but not efficacious (crude ACPR < 60%), an adaptation will be triggered to use an intermediate exposure of SJ733, obtained by pharmacoenhancement of a reduced dose of SJ733 (optional cohort 3). Due to the pharmacoenhancing effects of cobicistat, a co-dose of SJ733 (300 mg) + cobicistat (150 mg) is expected to yield a higher total plasma exposure (median AUC) of SJ733 than a dose of SJ733 (600 mg) alone (Figure 1). The increase in plasma exposure is expected to provide increased efficacy. While cohort 3 requires co-dosing with a pharmacoenhancer, if successful, this regimen would reduce the quantity of SJ733 required by two-fold, lowering cost of goods and potentially improving tolerability.

Cohorts 1a and 1b are expected to achieve roughly five-fold higher plasma exposure of (+)-SJ733 than Cohorts 2a and 2b. Thus, if Cohorts 1a and 1b prove efficacious but repeated drug-related adverse events are observed, the Investigator, DMC, and SRT may unanimously agree that no further patients should be recruited to Cohorts 1 but that patient recruitment to Cohorts 2 should still be pursued. In this scenario, the Investigator will assess the severity/intensity of the adverse reactions and clinical laboratory changes using the DMID Toxicity Grading Scale for Determining the Severity of Adverse Events provided in Protocol Attachment 3 and Section 8.1.2. This information will be relayed to the DMC and SRT, who will make recommendations regarding further conduct of the trial, and if considered necessary, may recommend pausing or stopping further administration of the investigational product. Cohort progression will only be explored if the Investigator, DMC, and SRT unanimously agree it is warranted and appropriate. These recommendations will also be communicated to the Ethics Committee and Regulatory Authority and any necessary updates will be made to the patient consent form.

Each cohort will consist of two treatment arms. Cohort progression for each treatment arm will be managed independently of the other treatment arm. For example, if data from the *P. falciparum* cohort (1A) do not meet the success criteria or are inconclusive, but the data from the *P. vivax* cohort (1B) do meet the success criteria, then the *P. vivax* arm may continue to explore reducing levels of SJ733 exposure according to Figure 1 (cohort 2B and 3B), while the *P. falciparum* initial cohort of the study will be expanded or terminated. Established antimalarial therapy will be given if a patient meets any of the defined treatment failure criteria. Finally, if one treatment arm meets the failure criteria, remaining patients who have not received treatment may be reassigned to the other treatment arm to improve statistical power.

Study Population

Men and women between the ages of 18 and 70 years with *P. falciparum* or *P. vivax* malaria monoinfection living in Peru. 2-6 cohorts of adult patients (10 patients per cohort) with acute, uncomplicated *P. falciparum* or *P. vivax* malaria monoinfection. In total, there will be a minimum of 20 and a maximum of 60 patients.

3. Data Elements

Endpoints

Primary endpoints related to efficacy

For *P. vivax:* Crude Adequate Clinical and Parasitological Response (ACPR) at Day 14 defined as the absence of microscopically determined parasitemia (thick smear) on Day 14, irrespective of axillary temperature, in patients who did not previously meet any of the criteria of early treatment failure, late clinical failure, or late parasitological failure.

For *P. falciparum:* Crude Adequate Clinical and Parasitological Response (ACPR) at Day 14 defined as the absence of microscopically determined parasitemia (thick smear) on Day 14, irrespective of axillary temperature, in patients who did not previously meet any of the criteria of early treatment failure, late clinical failure, or late parasitological failure.

Success criterion: Crude ACPR on Day $14 \ge 80\%$ (equivalent to $\le 20\%$ recurrence).

Primary endpoints related to safety and tolerability up to Day 42

- Incidence, severity, drug-relatedness, and seriousness of adverse events
- Proportion of patients with clinically significant abnormal laboratory values including changes from baseline (biochemistry and hematology)
- Proportion of patients with clinically significant abnormal vital signs including changes from baseline

• Proportion of patients with a decrease in hemoglobin (Hb): > 2 g/dL from baseline to an absolute value of < 5 g/dL

- Proportion of patients with an absolute Neutrophil count $< 1,000/\mu$ L after baseline
- Proportion of patients meeting Hy's law criteria
- Proportion of patients with the following LFT changes:
 - Any ALT or $AST \ge 5 \times ULN$
 - Any AST or ALT ≥ 3 x ULN together with the appearance of fatigue, nausea, vomiting, right upper quadrant pain or tenderness, fever, rash and/or eosinophilia (eosinophil percent or count above the ULN)
 - Persistent ALT $\ge 3 \text{ x}$ ULN for a period of more than 4 weeks.

• Proportion of patients with clinical signs of possible cutaneous adverse reactions such as dermatitis, rash, erythematous rash, macular rash, papular rash, maculo-papular rash, pruritic rash, pustular rash, vesicular rash

• Proportion of patients with clinically significant increases in venous methemoglobin levels

• Proportion of patients with significant changes in ECG findings, including heart rate, ECG intervals (PR, QTcB, QTcF), conduction changes or abnormalities

Success criterion: No repeated drug-related serious adverse events (Attachment 3, Section 8.1.2).

Secondary Endpoints

Secondary endpoints related to malaria signs and symptoms up to Day 42

- Proportion of patients with symptoms or physical examination signs related to uncomplicated *P. vivax* or *P. falciparum* malaria (dizziness, headache, nausea, anorexia, vomiting, diarrhea, pruritus, urticaria, skin rash, abdominal pain, joint pain, muscle pain, palpitations, sleep disturbance, confusion, hearing disturbance, visual disturbance, fatigue)
- Fever Clearance Time as defined as the time from baseline to the first of two consecutive post-dose axillary temperature measurements < 37.5°C obtained within an interval of 4 to 24 hours of each other.

Secondary endpoints related to secondary treatment outcomes

- Crude ACPR at Days 28, 35, and 42 (*P. vivax* or *P. falciparum*)
- Recurrence (*P. vivax* or *P. falciparum*) up to Day 42

Secondary endpoints related to parasite clearance kinetics by microscopy

- Parasite clearance time (PCT)
- PRR (parasite reduction rate) and parasitemia half life
- Times to microscopic clearance of asexual parasites
 - Total reduction (PC100)
 - 99% reduction (PC99)
 - 90% reduction (PC90)
 - 50% reduction (PC50)
- Microscopically determined percentage reduction in asexual parasites from baseline at:
 - 24 hours after administration of study drug
 - 48 hours after administration of study drug
 - 72 hours after administration of study drug
- Proportion of microscopically determined parasitemia in patients at:
 - 24 hours after administration of study drug
 - 48 hours after administration of study drug
 - 72 hours after administration of study drug

Secondary endpoints related to PK parameters up to Day 42

AUC_{0-t}, AUC_{0-inf}, C_{max}, t_{max}, t_½, Cl, F, etc.

Exploratory Endpoints:

- PCR-adjusted ACPR at Days 7, 14, 28, 35, and 42 (*P. vivax* or *P. falciparum*)
- PCR determined recurrence (*P. vivax* or *P. falciparum*) up to Day 42
- Correlation between parasite genotypes of interest and parasite clearance kinetics/efficacy

Data Sources

Data will be entered into REDCap instruments per the Data Management Plan (DMP). Clinical, laboratory, and safety study measures will be entered into the electronic data capture system (REDCap) and assessed for quality as outlined in the DMP.

Creation of Analysis Datasets and Analytic Data Handling

Data from REDCap will be exported and converted to SAS datasets. Analysis datasets will be created, and SAS programs will be developed to further investigate potential data issues via simple descriptive statistics and plots. Summary reports will be provided periodically during the course of the project to verify accuracy of data entry and provide early opportunities for clarification of questions and correction of errors and omissions.

For analysis datasets, Data Definition Tables (DDTs) are included to document all variables (both raw and derived) included in the analysis datasets. This includes the variable name, label, type, length, format, coded values and logic for creating derived variables. For raw data, a data dictionary is available through REDCap. The data dictionary provides a description of all data fields including the field name, label, field type, response option coding and branching logic.

Quality assurance strategies outlined in the DMP will be used to minimize missing data. In general, primary analyses will be conducted as observed. In the event imputation is needed and appropriate, it will be employed using multiple imputation methods. In the presence of imputation, the sample size is not diminished. A description of participant disposition will be included to assess incomplete data, visits, withdrawals, deviations, and discontinuations.

4. Statistical Methods

The overall study design is to demonstrate proof of concept and serves as an exploratory study. It is not intended to demonstrate superiority or non-inferiority against a control. Rather the goal is to establish preliminary data for planning future studies and to assess whether the SJ733 is safe and the observed curative rate equals or exceeds 80%. As such, there will be no statistical testing of hypotheses. This exploratory Proof of Concept study uses a fixed clinical safety and parasitological responses (primary endpoints) defined as the absence of any drug-related SAE or microscopically determined parasitemia 14-days after initiation of therapy in \geq 80% patients who did not violate any of the inclusion/exclusion criteria.

General Approach

The overall study design involves two cohorts receiving SJ733 doses (600 mg and 300 mg) with and without cobicistat (150 mg) as cohorts. Data subsets (eligible, evaluable and completer) will be used in the potential comparisons.

The primary analytic approaches will be descriptive. All data will be summarized descriptively for the appropriate analysis sets defined below: Continuous variables by descriptive statistics (number of patients [n], mean, standard deviation [SD], minimum, median, maximum); categorical data by absolute and relative frequencies (n and %) or contingency tables.

While this is a proof of concept, exploratory study, any potential comparisons between dose cohorts will be informative. Potential longitudinal data will be described as graphical summaries presented by each group. Unless indicated otherwise, summary statistics will be reported for observed data only, by dose cohort. Missing data will not be imputed. If a baseline value is missing, no change from baseline will be calculated.

Baseline is defined as the last observation prior to the administration of study medication.

SAS v9.4 or higher will be used for all analyses and a significance level of 0.05 will be used for all statistical tests.

Primary Analysis (Efficacy)

Primary analyses will be conducted across the two cohorts and by the two cohorts. Estimates will be presented with 95% confidence intervals.

The primary efficacy endpoints will be summarized descriptively, across the two cohorts and by the two cohorts. A statistical test will not be performed on the Crude ACPR on Day 14. Achieving a rate of 80% will be the decision rule for cohort dose phase. For future study planning, a one-sample z-test will be used to compare the rate of success, as defined by the Crude ACPR on Day 14, to the hypothesized rate of 80%.

Secondary efficacy variables will be summarized descriptively (by cohort; on Days 0, 14, 42) with proportions, means, and medians. To inform future studies, all estimates will be presented with 95% confidence intervals ($1.96 \pm$ margin of error). Graphical summaries will be used to describe changes in efficacy endpoints over time.

Exploratory Analysis

Exploratory model-based analyses will be performed as data allows. These will include model-based analyses of PK, PD and PK/PD.

Safety Analysis

Adverse events (AEs) will be summarized in Listing 9: Cumulative Summary of Adverse Events. The listing will include the following information: Patient ID, AE Description, Start Date, Stop Date, Special Interest, Severity, Relationship to Study Drug, Action Taken, Outcome of AE, Expected AE, and if the AE was a Serious Adverse Event (SAE).

Laboratory values that fall outside a clinically accepted reference range must be evaluated and commented on by the Investigator and graded according to the DMID Toxicity Scale for Determining Severity of Adverse Events (Protocol Attachment 3, Section 8.1.2).

All related AEs, AEs with outcome death, AEs leading to permanent discontinuation of treatment, SAEs and related SAEs will be summarized in Listing 10: Cumulative Summary of Serious Adverse Events. The listing will include the following information: Patient ID, Age, Sex, Dose, SAE Description, Start Date, Stop Date, SAE Category, and Relationship to Study Drug.

Treatment related AEs are those rated by the Investigator as "definite", "probable", "possible". In case relationship is unknown or missing the worst case will be assumed and the AE will be considered to be drug related

Planned Interim Analyses

Interim analyses will be made to review parasite reduction, adverse events, and clinical laboratory data. Following review, a decision on cohort progression will be made. However, as this is an exploratory study no formal analyses with adjustments for type I error are planned.

The following rules will be used as general guidelines to aid the decision of cohort progression:

- Curing ≥8/10 patients without any repeated drug-related SAEs then explore lower dose;
- Curing 6/10 or 7/10 patients without any repeated drug-related SAEs would be inconclusive and as a result we would expand the treatment arm;
- Curing $\leq 5/10$ is failure which would stop the trial in Cohort 1.

Strategies to Minimize Bias

Given the nature of the study, issues related to randomization/blinding/masking do not apply.

Sample Size Justification

The sample size for this exploratory Proof of Concept study was based on primary efficacy hypothesis. A one-sample z-test will have at least 85% power to detect the difference between the hypothesized curative rate (80%) with an alternative curative rate of 98%, assuming a one-sided significance level of 0.05, when the sample size is 20. All primary analyses will pool parasite arms within cohort dose. As such, a sample size of 10 patients per dose cohort arm was considered adequate to gain efficacy and safety data in patients with *P. falciparum* and *P. vivax* or to permit evaluation of MIC and MEC as

per similar studies conducted. If patients drop out for reasons unconnected to efficacy, attempts will be made to replace them to try to ensure the maximum number in each cohort.

5. Planned Tables, Listings, and Figures.

Number	Tables*
	*Tables will be provided overall and by cohort
Table 1	Patient Status
Table 2	Patient Demographics and Baseline Characteristics
Table 3	Malaria Sign and Symptoms
Table 4	Clinical Laboratory Summary
Table 5	Vital Signs
Table 6	12-LEAD ECG Summary
Table 7	Primary Endpoint
	Figures
Figure 1	Patient Status
Figure 2a	Efficacy: Asexual Parasite Count Over Time Up to Day 42 – Microscopist Report 1
Figure 2b	Efficacy: Asexual Parasite Count Over Time Up to Day 42 – Microscopist Report 2
Figure 3-	qPCR Values Over Time Up to Day 42
Figure 4a	Crude ACPR – Microscopist Report 1
Figure 4b	Crude ACPR – Microscopist Report 2
Figure 5	eDISH Plot
Figure 5a	Liver Testing by Patient
Figure 6	Total Bilirubin Lab Result (mg/dL) Over Time
Figure 7	Albumin Lab Result (g/dL) Over Time
Figure 8	ALT/SGPT Lab Result (U/L) Over Time
Figure 9	AST/SGOT Lab Result (U/L) Over Time
Figure 10	LDH Lab Result (U/L) Over Time
Figure 11	Alkaline Phosphate Lab Result (U/L) Over Time
Figure 12	Creatine Kinase Lab Result (mg/dL) Over Time
Figure 13a	Creatine Kinase Lab Result (mg/dL) Over Time for Males
Figure 13b	Creatine Kinase Lab Result (mg/dL) Over Time for Females
Figure 14	Urea Lab Result (mg/dL) Over Time
Figure 15	Sodium Lab Result (mmol/L) Over Time
Figure 16	Potassium Lab Result (mmol/L) Over Time
Figure 17	Glucose Lab Result (mg/dL) Over Time
Figure 18	Temperature (°C) Over Time – Overall
Figure 18a	Temperature (°C) Over Time – Day 1
Figure 18b	Temperature (°C) Over Time – Day 1-5
Figure 19	Leukocyte Total (/mm3) Over Time
Figure 20	Erythrocyte Count (/uL) Over Time
Figure 21a	Hemoglobin (g/dL) Over Time for Females
Figure 21b	Hemoglobin (g/dL) Over Time for Females
Figure 22a	Hematocrit (%) Over Time for Males
Figure 22 b	Hematocrit (%) Over Time for Females
Figure 23	Methemoglobin (%) Over Time
Figure 24	Platelet Count (/mm3) Over Time

Figure 25	Haptoglobin (mg/dL) Over Time
Figure 26	Neutrophil (/mm3) Over Time
Figure 27	Absolute Lymphocyte (/mm3) Over Time
Figure 28	Absolute Eosinophils (/mm3) Over Time
Figure 29	Absolute Basophils (/mm3) Over Time
Figure 30	Absolute Monocytes (/mm3) Over Time
Figure 31	Absolute Reticulocytes (%) Over Time
	Listings
Listing 1	Baseline Parasite Count
Listing 2	Efficacy: Asexual parasite count over time up to Day 42
Listing 3	qPCR Value over time up to Day 42
Listing 4	Fever Clearance Time
Listing 5	Medication History
Listing 6	Concomitant History
Listing 7	Malaria Signs and Symptoms
Listing 8	Definitive Antimalarial Treatment
Listing 9	Cumulative Summary of Adverse Events
Listing 10	Cumulative Summary of Serious Adverse Events

6. Planned Start and End of Analysis

Start of analysis: 05/2021 End of analysis: 12/2022

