or not tolerated, patients will receive standard treatment from the study physicians following the protocol for treating malaria according to current Peruvians standards (see Available Alternative Treatment).

Back to Top

Safety Precautions: Describe the procedures for protecting against or minimizing any potential risks, *including risks of breach of confidentiality or invasion of privacy*. Where appropriate, discuss provisions for ensuring necessary medical or professional intervention in the event of adverse events, or unanticipated problems involving subjects. Also, where appropriate, describe the provisions for monitoring the data collected to ensure the safety of subjects. If vulnerable populations other than adults with impaired consent capacity are to be recruited, describe additional safeguards for protecting the subjects' rights and welfare.

Established antimalarial therapy will be given if a patient meets any of the following criteria:

1) Clinical decline or lack of clinical improvement or decrease in platelets by > 20% for Patients with a platelet count at inclusion of between 50,000/mm3 and 74,999/mm3 (thrombocytopenia grade 2) or a drop in platelet count to < 50,000/mm3 for

Patients with a platelet count of > 75,000/mm3 at inclusion, at 24 hours for P. vivax malaria and 12 hours for P. falciparum malaria Patients with a = 25% increase in parasitemia in comparison to baseline with or without fever.

2) Development of any clinical complications (WHO definition of complicated/severe malaria, WHO [2013])

3) Parasitemia > 100,000/µL for P. falciparum at any time with or without fever

4) Parasitemia > baseline (from the slides taken 30 min before start of treatment) with or without fever, 48 hours after first dose for P. vivax and 36 hours after first dose for P. falciparum

5) Failure to clear all parasites by microscopy associated with axillary fever > 37.5°C between 72 hours and 7 days for P. vivax and 60 hours and 5 days for P. falciparum

6) Failure to clear all P. vivax parasites by microscopy with or without fever on Day 7 and P. falciparum parasites by microscopy with or without fever on Day 5

7) Patient exhibits a rise of microscopically detectable parasitemia between Day 7 and Day 42 with or without fever

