Following discharge, the patient will be monitored as an out-patient every 3-4 days: (on Days 7, 10 or 11, 14, 17 or 18, 21, 24 or 25, 28, and 35) until the final clinic visit on Day 42. At each visit the patient will be accompanied by the health care professional to Clínica de la Asociación Civil Selva Amazónica (ACSA) in Iquitos for the following examinations:

• Physical examinations and body temperature measurements will be conducted at every visit (Days 7, 10 or 11, 14, 17 or 18, 21, 24 or 25, 28, 35, 42).

• Blood samples will be taken for parasitology (microscopy and qPCR) at every visit (Days 7, 10 or 11, 14, 17 or 18, 21, 24 or 25, 28, 35, and 42).

• Additional blood samples for hematology and clinical chemistry assessments will be taken on Days 7, 14, 28, 35, and 42. After discharge (negative microscopy), and during the 42 day follow up period, if a study subject displays parasitological signs (as confirmed by positive microscopy) or develops clinical signs of malaria, he/she will be given standard of care according to the national treatment guidelines and supervised by the investigator.

Patient data will be logged into an Electronic Data Capture system at site by the site. Where the data violate validation checks queries will fire within the system for the Investigator to address and respond. Medications will be coded using the WHO-drug dictionary. Medical conditions and AEs will be coded using the latest version of the MedDRA dictionary.

When data entry has been completed and all outstanding queries have been resolved for a CRF, the CRF will be eligible for QC checking. A sample of 9 (i.e. ?n + 1) Patients will be selected for QC checks and 100% of these Patients' data will be audited. In addition, 100% of demography, parasite count, AEs and withdrawal data will be checked for all Patients. The highest acceptable error rate for QC is 0.5%. A higher error rate will prompt a review of a further sample of 9 Patients. If the error rate remains above 0.5%, a 100% QC check of all data will be conducted.

All errors discovered will be corrected on the database and the corrections will be audit-trailed and will undergo a QC check. On satisfactory completion of the QC checks, the database will be locked.

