Cohorts 1a and 1b are expected to achieve roughly five-fold higher plasma exposure of (+)-SJ733 than Cohorts 2a and 2b. Thus, if Cohorts 1a and 1b prove efficacious but repeated drug-related adverse events are observed, the Investigator, DSMB, and SRT may unanimously agree that no further patients should be recruited to Cohorts 1 but that patient recruitment to Cohorts 2 should still be pursued. In this scenario, the Investigator will assess the severity/intensity of the adverse reactions and clinical laboratory changes using the DMID Toxicity Grading Scale for Determining the Severity of Adverse Events provided in Attachment 3 and Section 8.1.2. This information will be relayed to the DSMB and SRT, who will make recommendations regarding further conduct of the trial, and if considered necessary, may recommend pausing or stopping further administration of the investigational product. Cohort progression will only be explored if the Investigator, DSMB, and SRT unanimously agree it is warranted and appropriate. These recommendations will also be communicated to the Ethics Committee and Regulatory Authority and any necessary updates will be made to the patient consent form.

Available Alternative Treatment(s): Describe alternative treatments and procedures that might be advantageous to the subjects, should they choose not to participate in the study. This should include a discussion of the current standard of care treatment(s).

The alternative is to not participate in the study and receive the standard medical attention currently available for the treatment of malaria. If the proposed experimental therapy is ineffective or not tolerated, patients will receive standard treatment from the study physicians following the standard protocol for treating malaria according to current Peruvians standards. Patients maintain the right to withdraw from the study and will receive the standard therapy at the conclusion of the study or at withdrawal to ensure resolution of their malaria. Even if the experimental therapy is effective, all patients will receive the standard therapy at the completion of the trial.

For P. falciparum mono-infection, a combination of Artesunate (AS) and Mefloquine (MQ), known as ASMQ, will be administered as two fixed dose tablets (100 mg AS and 200 mg of MQ) given daily for three consecutive days and supplemented with three tablets (15 mg each) of Primaquine phosphate (PQ) taken on the first day.

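### Read literally, Day 14 crude ACPR credits SJ733 with a smear-negative patient who was given rescue antimalarials without meeting a failure criterion

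*Combined protocol and SAP*

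**What the plan says.** **The endpoint.** SAP section 3, under the primary efficacy endpoints, uses one definition for both species. It requires "absence of microscopically determined parasitemia (thick smear) on Day 14, irrespective of axillary temperature", and it applies "in patients who did not previously meet any of the criteria of early treatment failure, late clinical failure, or late parasitological failure". The SAP Background and Study Design text repeats it. There are two conditions, and neither mentions another antimalarial.

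**Rescue tied to failure.** SAP Study Design, and Benefit vs. Risk in the IRB application, say: "Established antimalarial therapy will be given if a patient meets any of the defined treatment failure criteria". Safety Precautions in the IRB application lists seven triggers for established therapy. The first begins "Clinical decline or lack of clinical improvement or decrease in platelets by > 20" percent.

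**Rescue not tied to failure.** The IRB application has three other routes:
- Available Alternative Treatment(s): "If the proposed experimental therapy is ineffective or not tolerated, patients will receive standard treatment from the study physicians". Potential Risks and Benefit vs. Risk say the same in substance.
- The same section says that patients, who may withdraw at any time, "will receive the standard therapy at the conclusion of the study or at withdrawal to ensure resolution of their malaria".
- Safety Precautions, on follow-up after discharge: a patient who has positive microscopy "or develops clinical signs of malaria, he/she will be given standard of care according to the national treatment guidelines".

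**Use of the endpoint.** Under Planned Interim Analyses in the SAP, 8/10 or more leads to a lower dose, 6/10 or 7/10 is inconclusive and expands the arm, and 5/10 or fewer is failure.

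**Related rules.** Rescue treatment appears in the SAP outputs only as Listing 8. On replacement, Sample Size Justification in the SAP says "If patients drop out for reasons unconnected to efficacy, attempts will be made to replace them". Study Design in the IRB application allows replacement only when the reason is unconnected to safety as well as efficacy.

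**The concern.** Intolerance is named as a ground separate from inefficacy, so it need not be a treatment failure. Clinical signs after discharge are offered as an alternative to a positive smear, so treatment can start without parasites being seen. A patient switched to standard drugs by either route is likely to be smear-negative on Day 14. The clearance may then belong to the rescue drug, while the endpoint credits it to SJ733.

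The other half of the success rule does not catch this patient. It asks only for no repeated drug-related serious adverse event, so a switch for non-serious intolerance satisfies both halves.

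The error runs towards success and is most likely in a poorly tolerated or marginal regimen. A pass in Cohort 1 opens the lower-exposure regimen. A pass in Cohort 2 completes the trial under SAP Study Design, so the optional Cohort 3 would not be run.

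**Working it through.** **1. Trace one patient through the rules.** A patient stops SJ733 for non-serious intolerance, receives standard drugs, stays in follow-up and has a negative smear on Day 14.
- Smear condition: met.
- No earlier failure: met, since intolerance is not in itself one of the three failure types.
- Safety half of success: met, since there is no repeated drug-related serious adverse event.
- Missing-data rules: not engaged, since the smear was observed and SAP section 3 analyses primary data as observed.
- Analysis sets: General Approach in the SAP names eligible, evaluable and completer subsets, but the supplied text does not define them.

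Read literally, this patient is a responder. The same holds for treatment on clinical signs alone, unless that counts as late clinical failure.

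**2. The plan's own figure.** Sample Size Justification states at least 85% power for n = 20, 80% against 98%, one-sided 0.05. Power = Φ[(√20 × 0.18 − 1.645 × √(0.8 × 0.2)) / √(0.98 × 0.02)] = Φ[(0.805 − 0.658) / 0.14] = Φ(1.05) = 85.3%. It reproduces and does not depend on this point.

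**3. Effect on the pass mark.** Inputs: arm of 10 and pass mark 8 (SAP); true response p (60%, 70% and 80% used for illustration); k patients rescued for a non-failure reason (not in the documents; 1 or 2 assumed). The other patients respond independently with probability p.
- No such patient: P(X ≥ 8 of 10).
- k coded responder: P(X ≥ 8 − k of 10 − k).
- k coded non-responder: P(X ≥ 8 of 10 − k).

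At p = 0.6:
- k = 0: 45(0.6⁸)(0.4²) + 10(0.6⁹)(0.4) + 0.6¹⁰ = 0.120932 + 0.040311 + 0.006047 = 0.1673
- k = 1, responder: 36(0.6⁷)(0.4²) + 9(0.6⁸)(0.4) + 0.6⁹ = 0.161243 + 0.060466 + 0.010078 = 0.2318
- k = 1, non-responder: 0.060466 + 0.010078 = 0.0705

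| True response | k = 0 | k = 1, responder | k = 1, non-responder | k = 2, responder | k = 2, non-responder |
|---|---|---|---|---|---|
| 60% | 17% | 23% | 7% | 32% | 2% |
| 70% | 38% | 46% | 20% | 55% | 6% |
| 80% | 68% | 74% | 44% | 80% | 17% |

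**4. A single case.** Suppose seven of the nine other patients respond. With the rescued patient coded responder the arm is 8/10 and passes. Coded non-responder it is 7/10 and inconclusive.

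**The case against.** A reader might infer that the endpoint ignores rescue altogether. It does not: anyone rescued after meeting a defined failure is disqualified, and a negative Day 14 smear is still needed.

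A reader might also add the platelet and clinical-decline trigger to the gap. The documents do not support that. The Safety Precautions list is introduced in nearly the same words as the rule that SAP Study Design ties to the defined failure criteria, so the trigger most naturally belongs to those criteria.

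Nor do the documents say outright that the remaining patients are cures. A patient who withdraws may have no Day 14 smear, may be replaced, or may fall outside an undefined subset. The supplied text does not define early treatment failure, late clinical failure or late parasitological failure, and the full clinical protocol is an attachment that is not included. It may cover clinical signs after discharge, or other antimalarials more generally.

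There are safeguards too. The 8/10 rule is described as a guideline, progression is reviewed by the safety review team and the monitoring board, and Listing 8 shows who was treated.

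These points narrow the concern but do not remove it. The intolerance route remains open in the supplied text, and a listing does not change how the endpoint is counted.

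**Conclusion.** The concern holds in a limited form. The stated rule, followed literally, counts as a responder a smear-negative patient who received established antimalarial therapy before Day 14 without meeting a failure criterion. The supplied text allows this for intolerance and, unless late clinical failure covers it, for clinical signs after discharge.

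The number of such patients is unknown and may be zero. With one in ten, crediting that patient raises the chance of a pass by 6 to 8 percentage points at true rates of 60% to 80%. The coding choice matters more: at a true 80% it separates a 74% chance of passing from 44%. These figures assume that the rescued patient is smear-negative on Day 14 and that the others respond independently. The classification should be fixed in advance, not settled at a progression review with results in hand.

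**What to change.** Add to the ACPR definition, for both species and all time points: *A patient who received established (rescue) antimalarial therapy before the assessment day, for any reason, is not counted as an ACPR.*

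With it:
- Add a sensitivity analysis that excludes patients treated for non-failure reasons.
- Show these patients by reason (defined failure, intolerance, clinical signs without parasites) in Table 7 and at each progression review. Listing 8 already holds the data.
- Report incidental antibiotics with antimalarial activity separately, not as automatic failures. The eligibility criteria name several, such as azithromycin and the tetracyclines, and a patient already cleared by SJ733 could take one for an unrelated infection.
- Reconcile the two replacement rules so that these patients are not replaced out of the denominator.

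The cost is one sentence, some rows in Table 7 and one extra analysis. The downside is real: each such patient lowers observed ACPR by up to 10 points in an arm of 10 and can move 8/10 to inconclusive, which is why the sensitivity analysis is needed. Who receives rescue, and when, does not change.
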